9.5.1.1. Statistical Methods

No formal inferential statistics will be applied to the pharmacokinetic data.

The plasma concentration of PF-06755347 will be listed and summarized descriptively by nominal PK sampling time and treatment group. Individual participant, mean and median profiles of the plasma concentration-time data will be plotted by treatment group using actual and nominal times, respectively. Mean and median profiles will be presented on both linear and log scales.

If data allows, PK parameters will be descriptively summarized and plotted by treatment group.

If data permits, dose normalized (to 1 mg) AUC_{inf} , AUC_{last} and C_{max} will be plotted against dose (using a logarithmic scale), and will include individual participant values and the geometric means for each dose. These plots will be used to help understand the relationship between the plasma PK parameters and dose.

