Physical examination ^g	X	X																X	X	X	X	X	X	X	X			

Table 1. Schedule of Activities for IV cohorts

Protocol Activity	Screen		Clinical Confinement														Outpatient Follow-Up Visits										
	-56 to -2	-1 ^a	1														2	3	4	6	8	11 ±2	15 ±2	22 ±2	29 ±2	36 ^a ±3	50 ^a ±3
Hour(s) Post Dose			0 pre-dose	0.5	1 or EOI ^b	3 or EOI ^c	3.5	4	5	6	8	12	24	36	48	72	120	168	240	336	504	672	840	1176	1680		
Hematology & Coagulation (PT, INR, PTT, D-dimer & fibrinogen)	X	X			X ^{m,n}	X ⁿ			X ⁿ		X ⁿ	X ⁿ	X		X ⁿ	X	X	X	X	X	X	X	X	X	X		
Safety Labs					X ^{m,n}								X			X	X	X	X	X	X	X	X	X	X		
Chemistry/Urinalysis/Other Safety Labs	X	X			X ^{m,n}								X			X	X	X	X	X	X	X	X	X	X		
ECG ^h	X		X		X	X			X			X	X		X	X	X	X	X		X		X		X		
Telemetry		X ⁱ	X ⁱ	→	→	→	→	→	→	→	X																
Vital signs (BP, pulse rate, temperature) ^j	X		X	X	X	X	X ⁿ	X ⁿ	X	X ⁿ	X	X	X	X	X	X	X	X	X	X	X	X	X ⁿ	X	X ⁿ	X	
Pulse Oximetry	X		X	X	X	X	X ⁿ	X ⁿ	X	X ⁿ	X	X	X	X	X	X	X	X	X	X	X	X	X ⁿ	X	X ⁿ	X	
ADA blood sampling	X ^o	X																X		X			X		X		
CCI			█	█	█	█			█				█		█	█		█		█			█		█		
IV administration			X ^l	→	X	X																					
Infusion site assessment			X	X	X	X	X ⁿ	X ⁿ	X	X ⁿ	X	X	X					X ⁿ		X ⁿ			X ⁿ		X ⁿ		
PK blood sampling (IV Cohorts 1 and 2 only)			X		X	X			X		X	X	X	X	X	X	X	X									
PK blood sampling (IV Cohorts 3-5)			X		X	X			X		X	X	X		X	X	X	X		X	X	X	X	X	X		
PK blood sampling (IV Cohorts 5 exp. 6-9, and optional IV cohorts)			X		X ^{m,n}	X	X ⁿ	X ⁿ	X	X ⁿ	X	X	X		X	X	X	X		X	X	X	X	X	X		
Serious and non-serious Adverse Event monitoring	X	X	→	→	→	→	→	→	→	→	→	→	→	→	→	→	→	→	→	→	→	→	→	→	X		
Prior/Concomitant treatments	X	X	X										X	→	→	→	→	→	→	→	→	→	→	→	X		

Abbreviations: →= ongoing/continuous; ADA= anti-drug antibody; BP = blood pressure; ECG = electrocardiogram; EOI = end of infusion; HepBsAg = hepatitis B surface antigen; HepBcAb = hepatitis B core antibody; HCVAb = hepatitis C antibody; HIV = human immunodeficiency virus; IgA = immunoglobulin A; IgG = immunoglobulin G; INR = international normalized ratio; IV = intravenous; PK = pharmacokinetics; PT = prothrombin time; PTT = partial thromboplastin time; RNA = ribonucleic acid; TB = tuberculosis; T3 = triiodothyronine; T4 = thyroxine; TSH = thyroid stimulating hormone; TSAb = thyroid stimulating antibodies.

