9.5. Pharmacokinetic Analysis

9.5.1. Derivation of Pharmacokinetic Parameters

PK parameters following single dose administration will be derived from the plasma PF-06755347 concentration-time profiles as defined in [Table 10](#) for each participant and treatment, as applicable, using noncompartmental analysis of concentration-time data. Samples below the lower limit of quantitation will be set to zero for analysis. Actual sample collection times will be used for the pharmacokinetic analysis.

Table 10. Plasma Pharmacokinetic Parameter Definition

Parameter	Definition	Mode of Determination
C_{max}	Maximum plasma concentration	Observed directly from data
C_{max} (dn)	Dose normalized C_{max}	$C_{max}/Dose$
T_{max}	Time for C_{max}	Observed directly from data as time of first occurrence
AUC_{last}	Area under the plasma concentration-time profile from time zero to the time of last quantifiable concentration (C_{last})	Linear/Log trapezoidal method
AUC_{last} (dn)	Dose normalized AUC_{last}	$AUC_{last}/Dose$
AUC_{inf}^a	Area under the plasma concentration-time profile from time zero extrapolated to infinite time	$AUC_{last} + (C_{last}^*/k_{el})$, where C_{last}^* is the predicted plasma concentration at the last quantifiable time point estimated from the log-linear regression analysis
AUC_{inf} (dn) ^a	Dose normalized AUC_{inf}	$AUC_{inf}/Dose$
$t_{1/2}^a$	Terminal half-life	$\text{Log}_e(2)/k_{el}$, where k_{el} is the terminal phase rate constant calculated by a linear regression of the log-linear concentration-time curve. Only those data points judged to describe the terminal log-linear decline will be used in the regression.
CL (IV) ^a	Systemic Clearance	$Dose/AUC_{inf}$
V_{ss} (IV) ^a	Volume of distribution at steady-state	$CL * MRT$ where $MRT = (AUMC_{inf}/AUC_{inf}) - (DOI/2)$
CL/F (SC)	Apparent clearance	$Dose/AUC_{inf}$ for SC route
V_z/F (SC)	Apparent volume of distribution	$Dose / (AUC_{inf} * k_{el})$ for SC route
F (SC)	bioavailability	$F = AUC_{inf,sc} / AUC_{inf,iv}$

a. If data permit.

Abbreviation: AUMC = area under the first moment plasma concentration curve; dn=dose normalized to a 1 mg dose; DOI = duration of infusion; MRT = mean residence time.

Actual PK sampling times will be used in derivation of PK parameters.

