8.2. Statistical Analyses

8.2.1. Pharmacokinetic Analysis

To assess the pharmacokinetics of PF-06755347, the PK parameters detailed in Section 6.3 will be listed and summarized for subjects in the PK analysis set (as defined in [Section 5.2.2](#)). Missing values will be handled as detailed in [Section 7](#). Each PK parameter will be summarized by dose. Optional Cohort 10 Japanese (if applicable) will be analysed separately. Each summary will include the set of summary statistics as specified in [Table 2](#).

Table 2. PK Parameters to be Summarized Descriptively

| Parameter | Summary Statistics |
|--|--|
| AUC _{last} , AUC _{inf} , C _{max} , C _{max} (dn), AUC _{last} (dn), AUC _{inf} (dn), CL, V _{ss} , | N, arithmetic mean, median, cv%, standard deviation, minimum, maximum, geometric mean and geometric cv%. |
| T _{max} | N, median, minimum, maximum. |
| t _{1/2} | N, arithmetic mean, median, cv%, standard deviation, minimum, maximum. |

There will be one summary table split by dose presenting all PK parameters.

To assess the relationship between the PK parameters and dose, dose normalized AUC_{inf} (if data permit), AUC_{last} and C_{max} will be plotted against dose (using a logarithmic scale), and will include individual subject values and the geometric means for each dose separately. Geometric means will have a different symbol than the individual values. The values will be dose normalized (to a 1 mg dose) by dividing the individual values and raw geometric means by dose. A footnote will be added to the plots to indicate that geometric means are presented.

Supporting data from the estimation of t_{1/2} and AUC_{inf} will be listed where applicable: terminal phase rate constant (k_{el}); goodness of fit statistic from the log-linear regression (r²); the percent of AUC_{inf} based on extrapolation (AUC_{extrap}%); and the first, last, and number of time points used in the estimation of k_{el}. These data may be included in the clinical study report.

Presentations for PF-06755347 concentrations will include:

- A listing of all concentrations sorted by subject ID, dose, and nominal time post-dose. The concentration listing will also include the actual times. Deviations from the nominal time will be given in a separate listing.

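### Dose-normalised AUClast is plotted against dose across unequal IV sampling windows, which can pull down the two lowest doses; a fixed-window AUC168 plot should be added

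*Protocol*

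**What the plan says.** - **Plots.** Protocol Section 9.5.1.1 states "No formal inferential statistics will be applied to the pharmacokinetic data". The sentence that opens "If data permits, dose normalized (to 1 mg" then lists AUCinf, AUClast and Cmax for plotting against dose, with the purpose "These plots will be used to help understand the relationship between the plasma PK parameters and dose".
- **SAP.** Section 8.2.1 has the same plots, introduced by "To assess the relationship between the PK parameters and dose, dose normalized". They "will include individual subject values and the geometric means for each dose separately". In that sentence only AUCinf is conditional on the data, but SAP Table 1 also marks dose-normalised AUClast as conditional.
- **AUClast.** Protocol Table 10 defines it as "Area under the plasma concentration-time profile from time zero to the time of last quantifiable concentration". It therefore depends on the sampling schedule and on the assay limit.
- **Schedule.** In protocol Table 1, the row "PK blood sampling (IV Cohorts 1 and 2 only" has its last mark at 168 h. The row "PK blood sampling (IV Cohorts 3-5" continues from 168 h to 336 h and beyond. Footnote a ends follow-up at about Day 36 for IV doses up to 1 mg/kg. Section 2.1 closes IV dosing, and the highest IV dose in Table 6 is 1 mg/kg, so Day 71 applies only to SC cohorts.
- **AUC168.** It is the metric of the PK stopping limit (protocol Section 6.7) and of Table 6. It is absent from protocol Table 10, from SAP Tables 1 and 2, and from the planned plots.

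**The concern.** When PK is linear, dose-normalised AUC should be flat across doses, provided every dose is measured over the same time. Here the two lowest IV doses are cut at 168 h (7 days) and the other IV doses at about 840 h (35 days). A drug with a slow terminal phase would then show dose-normalised AUClast rising with dose even if its kinetics were linear. Neither document sets a common window for the plot or warns the reader.

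At stake is the reported dose-exposure relationship, because these plots are the only planned look at it. The protocol expects some non-linear kinetics (Sections 2.2.2 and 4.2.1.1), so a schedule effect would be mixed with something that may be real. Section 9.5.1.1 also does not say whether IV and SC results share an axis.

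**Working it through.** **Inputs.** Windows of 168 h and 840 h (protocol Table 1 and footnote a). Terminal half-life predicted at 8-9 days, or 192-216 h (Section 4.2.1.1). Section 2.3 puts about 3 half-lives before discharge on Day 8, which implies 168/3 = 56 h. Observed Cmax and AUC168 come from Table 6. Cohort 5 is 1 mg/kg (Table 8). That Cohorts 1-4 are 0.01, 0.03, 0.1 and 0.3 mg/kg is inferred from the order of Tables 6 and 8.

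**1. Reproduce Table 6.** 34000/AUC168 gives 24113, 3238, 752, 245, 121 and 69. 1130/Cmax gives 10089, 2534, 685, 240, 91 and 46. All agree with the table.

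**2. Effect of the window under exact proportionality.** For mono-exponential decline the share of AUCinf captured by time T is f(T) = 1 - 2^(-T/t½). The share of the 840-h AUC captured by 168 h is f(168)/f(840).

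| t½ | f(168) | f(840) | ratio | deficit | apparent six-dose log-log slope |
|---|---|---|---|---|---|
| 56 h | 0.875 | 1.000 | 0.875 | 12.5% | 1.03 |
| 192 h | 0.455 | 0.952 | 0.478 | 52% | 1.19 |
| 216 h | 0.417 | 0.932 | 0.447 | 55% | 1.20 |

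For a given terminal half-life these are upper limits, because a fast early phase puts more of the AUC before 168 h. By the same formula f(840)/f(1680) is 1.00 at 56 h and 0.95-0.94 at 192-216 h, so Day 36 against Day 71 matters little.

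**3. How far the data sit from that worst case.** Mono-exponential decline implies AUC168/Cmax = (t½/ln 2) × f(168), which is about 71 h at 56 h and 126-130 h at 192-216 h. Table 6 gives 12.6, 23.5, 27.4, 29.6, 22.7 and 19.8 h. Much of the exposure falls early, so the true deficit is probably smaller.

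**4. What an equal window already shows.** AUC168 divided by the mg/kg dose is 141, 350, 452, 463, 401 and 490. Against the geometric mean of the four higher doses (451), the two lowest are at 141/451 = 31% and 350/451 = 78%. The log-log slope is 1.21 over six doses, 1.06 from 0.03 mg/kg up and 1.00 from 0.1 mg/kg up. Cmax/dose, which the window cannot affect, also rises: 11.2, 14.9, 16.5, 15.7, 17.7, 24.7. These are single summary values per dose, so the slopes carry no confidence interval.

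**5. The two effects together.** Multiplying step 4 by the step 2 ratios, 0.03 mg/kg could read on AUClast as low as 78% × 0.875 = 68% at 56 h, or 78% × 0.447 = 35% at 216 h. For 0.01 mg/kg the figures are 27% and 14%.

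**6. Assay limit.** Spreading AUC168 over a mono-exponential bounds the 168-h concentration at about 0.002-0.006 µg/mL for 0.01 mg/kg and 0.019-0.046 µg/mL for 0.03 mg/kg (half-lives of 56 h and 204 h). The LLOQ is not stated. If it lies above these values, the assay ends AUClast before the schedule does, and the schedule adds no bias.

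**7. Route.** For the 25 mg SC entry in Table 7, 98.5/168 = 0.586, which matches the Cav in Section 4.2.1.3.3, so that entry covers 168 h. The 50 and 100 mg entries are assumed to do the same. SC AUC per mg is 98.5/25 = 3.9, 159/50 = 3.2 and 315/100 = 3.2. IV at 0.3, 0.7 and 1 mg/kg, at an assumed 70 kg, gives 139/21 = 6.6, 281/49 = 5.7 and 490/70 = 7.0 (about 4.5-9.8 over 50-90 kg). The mg ranges overlap, so a shared panel would mix route with dose.

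**The case against.** The plots are descriptive, with no slope, interval or proportionality criterion. AUClast is one of three metrics: Cmax is immune to the window, and AUCinf corrects for it where it can be estimated. That stands. AUCinf is only a partial safeguard, however. In the step 2 model a profile ending at 168 h needs 1 - f(168) = 12.5% extrapolation at a 56-h half-life and 55-58% at 8-9 days. The protocol reports the extrapolated percentage but sets no limit on it.

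A reader might go further and infer any of the following. The documents do not support them.

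- **That escalation is distorted.** The limits in Section 6.7 use individual AUC168 and Cmax, and IV dosing has ended.
- **That the schedule creates a false non-linearity.** The low values at the lowest doses are present in an equal window, and Cmax/dose rises too. Assay truncation or real non-linear clearance could explain them.
- **That AUClast is the only AUC certain to be plotted.** The condition in protocol Section 9.5.1.1 opens the sentence on all three metrics, and SAP Table 1 also makes dose-normalised AUClast conditional.
- **That AUClast should be dropped.** It is a declared endpoint (protocol Section 3), and the SC cohorts share one schedule to Day 71.
- **That IV and SC will certainly be pooled.** The protocol is silent, and the SAP describes IV dosing only.

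**Conclusion.** The point holds as a limited bias in a descriptive plot. Unequal scheduled windows can lower dose-normalised AUClast at the two lowest IV doses by at most 12.5% (half-life 56 h) or 52-55% (8-9 days), and by nothing if concentrations fall below the LLOQ before 168 h. The range is wide because the protocol gives two half-lives that disagree. The upper end also rests on mono-exponential decline, which the observed AUC168/Cmax values contradict.

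The bias runs in the same direction as the shortfall already visible over 168 h (31% and 78% of the higher doses). The AUClast plot alone therefore cannot tell schedule from pharmacology, whereas a fixed-window plot removes the schedule part. It would not make the low-dose shortfall disappear. The conclusion assumes that Cohorts 1-2 are 0.01 and 0.03 mg/kg, and that the column positions in Table 1 were read correctly from extracted text.

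**What to change.** - Add AUC168 and dose-normalised AUC168 to protocol Table 10 and SAP Tables 1 and 2.
- In protocol Section 9.5.1.1 and SAP Section 8.2.1, add a plot of dose-normalised AUC168 against dose. Keep Cmax, AUClast and, if data permit, AUCinf.
- Show IV and SC in separate panels.
- Footnote the AUClast plot with the sampling window of each cohort.

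The cost is some wording and one more derived parameter. Every cohort has a scheduled PK sample at 168 h, and AUC168 is already calculated for the stopping limit, so no new samples are needed. Label: free improvement.

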9.6. Pharmacodynamic Analysis

Baseline and change from baseline in cytokines and complement components will be summarized descriptively and plotted by dose. CCI

Further details will be documented in the SAP.

9.7. Analysis of Other Endpoints

Immunogenicity (ADA) results will be listed (including titers) and summarized by treatment group and time points. Participant level immune response will also be summarized by treatment. Effect of positive ADA on safety, PD and PK will be assessed, if appropriate.

Pharmacogenomic data will be collected and retained for future analyses, but will not be analyzed, specifically, for this study.

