4. STUDY DESIGN

4.1. Overall Design

This is a Phase 1, randomized, double-blind, Sponsor-open, placebo -controlled, first-in-human single -ascending dose study to evaluate the safety, tolerability, and PK of PF-06755347 in healthy adult male participants by IV and SC administration and in male or female participants with persistent or chronic ITP by SC administration. Personnel, trained in advanced cardiac life support, emergency resuscitative equipment and the management of anaphylaxis, are immediately available to treat systemic reactions under the supervision of a physician. IV fluids, epinephrine, antihistamine and methylprednisolone will be available for immediate parenteral use in the event of an anaphylactic reaction.

A schematic of the overall study design is provided in [Section 1.2](#) (note actual dose levels to be administered beyond the starting dose are subject to change, see [Section 4.2.1.3](#)). A total of approximately 75 healthy adult male participants are planned to be randomized to either receive PF-06755347 or placebo by intravenous or subcutaneous administration in a 3:1 allocation ratio. All participants with ITP will receive PF-06755347. Clinical data from the IV cohorts supporting the transition to SC dosing are summarized in the IB, Section 6. SC Cohorts 7-14 are planned, Cohort 7 will have 4 male participants (3 active and 1 placebo)

and Cohorts 9-11 will have 8 male participants (6 active and 2 placebo). Cohort 12 (optional Japanese cohort) will include approximately 4-8 male Japanese healthy participants and Cohorts 13 and 14 combined will include a maximum of 12 male or female participants with ITP. The total number of participants randomized will not exceed 87. The ITP cohort dosing will start after completion of the 50 mg dose cohort in HPs.

Participants within each cohort will be dosed using a sequential dosing scheme. For all cohorts, only a single participant will be dosed at any given time. Based on the emerging safety data to date with IV dosing, cytokine and laboratory abnormalities reach their peak levels within the first few hours following PF-06755347 C_{max} and are resolved within 24 hours. The C_{max} was predicted to be 24 -48 hours with SC administration, however preliminary data from Cohort 7 supports increasing the monitoring period to 96-hr for safety.

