6.2.1. Adverse Events

Any events occurring following start of treatment or increasing in severity will be counted as treatment emergent.

Events that occur in a non-treatment period (for example, washout or follow-up) will be counted as treatment emergent and attributed to the previous treatment taken.

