- A summary of concentrations by dose, cohort, and nominal time post-dose, where the set of statistics will include n, mean, median, standard deviation, coefficient of variation (cv), minimum, maximum and the number of concentrations above the lower limit of quantification.
- Median concentrations time plots (on both linear and semi-log scales) against nominal time post-dose by dose and cohort (all doses on the same plot per scale, based on the summary of concentrations by dose, cohort and time post-dose).
- Mean concentrations time plots (on both linear and semi-log scales) against nominal time post-dose by dose and cohort (all doses on the same plot per scale, based on the summary of concentrations by dose, cohort and time post-dose).

The length of time used for the x-axes of these plots will be decided on review of the data, and will depend on how long PF-06755347 concentration is quantifiable in the matrix.

For summary statistics, median and mean plots by sampling time, the nominal PK sampling time will be used, for individual subject plots by time, the actual PK sampling time will be used.

Subjects having positive ADA may be analyzed separately to assess impact of ADA on PK concentrations and if no effect then those subjects will be included in the summarized PK concentration and parameter descriptive statistics. Refer to [Section 8.3.8](#) for more details.

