8.3.8. Other Safety Data

The percentage of subjects with positive ADA will be summarized by dose and presented separately for Cohort 10 (if applicable). For subjects with positive ADA, the magnitude (titer), time of onset, and duration of ADA response will also be described, if data permit. The impact of ADA on PK and/or safety may also be assessed, if data permit. This may include:

- Spaghetti plots of individual PF-06755347 concentration time profile, grouped by ADA status, produced separately by treatment and for Cohort 10 (if applicable).
- Table summaries of PK parameters (AUC_{inf} , AUC_{last} and C_{max}) by ADA status, presented separately for Cohort 10 (if applicable).

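### The SAP 8.3.8 tables of Cmax and whole-profile AUC by ADA status say little about ADA that develops after dosing; pre-existing and treatment-emergent ADA should be separated

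*Protocol*

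**What the plan says.** Protocol 9.7 promises an assessment without a method: "Effect of positive ADA on safety, PD and PK will be assessed, if appropriate". SAP 8.3.8 makes it optional: "The impact of ADA on PK and/or safety may also be assessed, if data permit". It then lists two displays that this may include:

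- "Spaghetti plots of individual PF-06755347 concentration time profile, grouped by ADA status", by treatment.
- "Table summaries of PK parameters" by ADA status. The parameters named are AUCinf, AUClast and Cmax; CL and half-life are not among them, although SAP Table 1 derives both.

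For ADA-positive participants, titer, "time of onset, and duration of ADA response will also be described, if data permit". Onset is not linked to the PK displays.

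SAP 8.2.1 adds: "Subjects having positive ADA may be analyzed separately to assess impact of ADA on PK concentrations". If no effect is seen, these participants stay in the PK summaries. No criterion for absence of an effect is given.

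In Protocol Tables 1-3, ADA is sampled on Day -1 and then at 168, 336, 840 and 1680 h. IV cohorts at or below 1 mg/kg finish at about Day 36 (840 h). PK sampling runs to 1680 h in the SC cohorts but ends at 168 h in IV Cohorts 1 and 2. Protocol 5.2 and 5.4 contain no ADA exclusion, so participants may be ADA-positive at dosing. SAP 6.6.1 leaves the definition of a positive result to assay validation and a possible SAP amendment.

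**The concern.** Grouping by ADA status alone puts two kinds of participant in one column. Antibodies present at dosing can alter the whole profile, including Cmax. Antibodies that form after a single dose can alter only the exposure still to come. For the second kind, the tables sort participants by an event that follows much or all of the outcome being compared. A Cmax difference between those groups could not be read as an effect of ADA. A real effect on clearance would be averaged with exposure that accrued before any antibody existed.

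The likely result is an apparent lack of effect even if ADA speeds elimination. Immunogenicity is a secondary objective. The SAP 8.2.1 decision on whether ADA-positive participants stay in the PK summaries also needs a view on ADA impact that looks at the right part of the profile.

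**Working it through.** **Step 1. Reproduce the plan's figure.** Protocol 4.2.1.3.3 gives an observed Cav of 0.586 µg/mL after 25 mg SC; Table 7 gives an AUC of 98.5 µg·hr/mL. 98.5/168 = 0.586, whereas 98.5/576 = 0.171. The 25 mg entry is therefore AUC to 168 h, the period before the first post-dose ADA sample. I read the 50 and 100 mg entries the same way.

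**Step 2. Cmax.** IV infusions last about 1 to 3 h (Protocol Table 8), so Cmax is expected near the end of infusion. For SC, Protocol 4.1 gives a predicted 24-48 h and adds that "preliminary data from Cohort 7 supports increasing the monitoring period to 96-hr for safety". Both precede 168 h. No individual Tmax values are given.

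**Step 3. Share of AUCinf accrued by 168 h.** The protocol supports two half-lives:
- Section 2.3 equates Day 8 with about 3 half-lives: 168/3 = 56 h.
- Section 4.2.1.1 predicts 8-9 days: 192-216 h.

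IV share accrued = 1 − 2^(−168/t½). For SC (first-order absorption), ka is solved from Tmax = ln(ka/ke)/(ka − ke), and the share still to come after T is (ka·e^(−ke·T) − ke·e^(−ka·T))/(ka − ke).

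| Half-life | IV | SC, Tmax 24 h | SC, Tmax 48 h | SC, Tmax 96 h |
|---|---|---|---|---|
| 56 h | 87.5% | 85.7% | 80.1% | 51.4% |
| 192 h | 45.5% | 44.2% | 42.2% | 35.6% |
| 216 h | 41.7% | 40.5% | 38.7% | 33.1% |

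The range is about 33% to 87.5%.

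Table 7 narrows this for SC. AUC168/(Cmax × 168) is 98.5/(0.895 × 168) = 0.655, 159/(1.37 × 168) = 0.691 and 315/(2.64 × 168) = 0.710. One-compartment profiles that match these ratios have 29-39% of AUC after 168 h with Tmax 24 h. With Tmax 48 h they have 18% and 23% (0.691 and 0.710 only; 0.655 has no solution). No solution exists for Tmax 72 or 96 h. Matched models therefore put 61-82% before 168 h, and the 33% end is a limit, not an expectation.

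**Step 4. How much an effect would move each measure.** Suppose, for illustration, that ADA doubles clearance from time T. Cmax does not change. AUCinf falls by half of what was still to come:
- T = 168 h, IV: 0.125/2 = 6% to 0.583/2 = 29%.
- T = 168 h, SC: 0.143/2 = 7% to 0.669/2 = 33%.
- T = 336 h, IV: 2^(−336/56)/2 = 0.8% to 2^(−336/216)/2 = 17%.

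Under the same assumption (IV, constant volume), the concentration 168 h after onset is 2^(−168/t½) of its value without ADA, that is 12.5% to 58%. This is a fall of about 42% to 87.5%. Concentrations after onset respond far more than AUCinf does.

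**Step 5. IV Cohorts 1 and 2.** PK sampling ends at 168 h. For anyone negative at 168 h and positive later, all of AUClast precedes onset and the profile plot has no post-onset points.

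**The case against.** The strongest reply is that the SAP already looks at concentrations over time. A reader might infer from the tables that the plan cannot detect an ADA effect; the documents do not support that. The profile plots by ADA status reach past 168 h wherever PK sampling continues, AUC includes some post-onset exposure, and Day -1 positives can show an effect on Cmax and on the full AUC. A first positive at 168 h also shows only that onset was no later than 168 h.

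Three further inferences should be resisted:

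- **The Cmax and AUC tables decide who enters the PK summaries.** SAP 8.2.1 rests that decision on PK concentrations. What remains is that it gives no criterion and does not confine the assessment to samples after onset.
- **Adverse events will be compared by ADA status.** No such table is specified. Protocol 9.7 and SAP 8.3.8 mention safety only in general terms. SAP 6.2.1 defines treatment emergence relative to dosing: "Any events occurring following start of treatment or increasing in severity will be counted as treatment emergent". The gap is the absence of a timing rule if the comparison is made.
- **Every Cmax precedes 168 h.** This is expected, but it cannot be verified without individual Tmax values.

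It is also fair that this is optional, descriptive work in a study without hypothesis tests, that the secondary endpoint is ADA incidence and not ADA effect, and that the SAP was written for the IV-only design. The model is simple: Protocol 4.2.1.1 uses two compartments with non-linear clearance, and its 8-9 days is a prediction. These points limit the weight and precision of the finding. They do not change the order of events, nor the fact that the two kinds of ADA are not separated.

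**Conclusion.** The point holds in limited form, as a change that should be made. For treatment-emergent ADA, the Cmax table is uninformative and the whole-profile AUC tables are diluted toward no effect. About 33% to 87.5% of AUCinf precedes the first post-dose ADA sample across the protocol's two half-lives, or 61-82% in models matched to the observed SC data. The shares assume one compartment; the effect sizes also assume a doubling of clearance. With 3 to 6 active participants per SC cohort (Protocol 4.1 and Table 4), AUC changes of the size shown would be hard to see. The profile plots are a partial safeguard, weakened because onset is not marked and because they stop at 168 h in IV Cohorts 1 and 2. The tables remain useful for ADA present on Day -1.

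**What to change.** In SAP 8.3.8, with a cross-reference from 8.2.1:

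1. Classify ADA as pre-existing (Day -1 positive) or treatment-emergent, with onset bracketed by the last negative and first positive sample.
2. Limit the Cmax, AUClast and AUCinf tables by ADA status to Day -1 status.
3. For treatment-emergent ADA, mark onset on the individual profiles. Where samples exist, compare concentrations or terminal slope from the first positive sample onward with ADA-negative participants of the same dose, route and visit. Use this comparison for the SAP 8.2.1 inclusion decision.
4. If safety by ADA status is assessed, list each event's start relative to the last negative and first positive ADA samples, and do not attribute events in the interval between them to ADA. For someone negative on Day -1 and positive at 168 h, every event from dosing to 168 h falls in that interval.

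Protocol 9.7 can stand as worded. The amendment foreseen in SAP 6.6.1 is a natural place for the change. The cost is SAP wording and minor programming, with no new samples. The downside is small: few post-onset concentrations may be quantifiable, especially if the half-life is near 56 h, so the comparison stays descriptive.
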